#### Secondary Endpoints

1. The proportion of subjects with endoscopic improvement, defined as an Endoscopic Response Score of 0 or 1, with at least a 1 point reduction from baseline in the endoscopic score at Week 8

2. The proportion of subjects in clinical remission at Weeks 2, 4, and 8, defined as a score of 0 for rectal bleeding and 0 or 1 with at least 1 point decrease from baseline for stool frequency in the Clinical Response Score subset
3. Time to normal stool pattern, defined as time in days from randomization to the first day of 3 consecutive days with a stool frequency score of 0, based on subject daily diary
4. The change from baseline in rectal bleeding score at Weeks 2, 4, and 8, based on subject daily diary
5. The change from baseline in serum CRP levels at Weeks 2, 4, and 8
6. The change from baseline in fecal calprotectin levels at Week 8
7. The change from baseline to each scheduled assessment for published and validated domain scores of the IBDQ
8. Safety, assessed by incidence and severity of AEs and abnormal laboratory values

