### **3.2 Planned Number of Trial Sites and Subjects**

This trial will be conducted at approximately 110 sites in North America and Europe. Approximately 220 subjects with active, mild to moderate UC will be randomized to receive mesalamine 4 g extended release granules (sachet) or matching placebo in a 1:1 ratio (110/treatment regimen).

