### 9.1 Determination of Sample Size

The true remission rates at Week 8 for mesalamine 4 g extended release granules (sachet) and placebo regimens were assumed as 36% and 18%, respectively, based on Kamm (2007) (3), Lichtenstein (2007) (4), and Marteau (2005).(5) Under these assumptions, a sample size of 110 randomized subjects per group will provide at least 85% power to detect a statistically significant treatment group difference in the remission rate at a two-sided 0.05 significance level using the chi-square test.

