### **9.6.2 Primary Endpoint**

The primary efficacy analysis will be based on all randomized subjects (ITT analysis set). The proportion of subjects with remission, defined as rectal bleeding score of 0 and stool frequency score of 0 or 1 with at least 1 point decrease from baseline, with an endoscopic score of 0 or 1 in the Clinical and Endoscopic Response Score at Week 8, will be compared between treatment groups using the chi-square test at a two-sided 0.05 significance level. Subjects who discontinue the double-blind regimen before Week 8, as well as subjects with missing remission assessment at Week 8, will be considered not having achieved remission. The odds ratio will be estimated and its 95% confidence interval will be provided.

The following sensitivity analyses will be conducted to assess the robustness of the primary analysis:

- As-treated analysis based on actually received treatment
- Analysis on the mITT analysis set
- Analysis on the PP analysis set
- Assessment of the homogeneity of odds ratios across geographical regions, baseline demographic characteristics, and baseline disease characteristics
- Analysis on the last observed Clinical and Endoscopic Response Score
- Analysis using multiple imputation methods for missing remission assessment at Week 8
- Analysis using pattern mixture models for missing remission assessment at Week 8

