The proportion of subjects in clinical remission at Weeks 2, 4, and 8 will be analyzed by the generalized estimating equations approach as longitudinal binary outcomes. The model will include treatment, time, and treatment- by-time interaction. The clinical remission rates and odds ratios will be estimated for each time point.

The time to normal stool pattern will be analyzed using the same statistical method used for the analysis of the time to cessation of rectal bleeding.

The change from baseline in rectal bleeding score and serum CRP levels at Weeks 2, 4 and 8 will be analyzed by repeated-measures analysis of covariance (ANCOVA) models that include treatment, time, and treatment-by-time interaction as fixed effects, and the corresponding baseline value as a covariate based on the observed data. The adjusted changes from baseline and their difference between treatment groups will be estimated for each time point. The change from baseline in the fecal calprotectin level at Week 8 will be analyzed by an ANCOVA model that includes treatment as a factor and baseline value as a covariate.

The efficacy data captured during the 8-week open-label mesalamine 4 g/day treatment period, will be used for exploratory purposes only.

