9.3.2 Other Secondary Endpoints

The following secondary endpoints will be analyzed for the ITT analysis set.

- The proportion of subjects with endoscopic improvement, defined as an Endoscopic Response Score of 0 or 1, with at least a 1 point reduction from baseline in the endoscopic score at week 8
- The proportion of subjects in clinical remission at Weeks 2, 4, and 8, defined as a score of 0 for rectal bleeding and “0” or “1 with at least 1 point reduction from baseline” for stool frequency in the Clinical Response Score subset
- Time to normal stool pattern, defined as time in days from randomization to the first day of 3 consecutive days with a stool frequency score of 0, based on subject daily diary
- The change from baseline in rectal bleeding score at Weeks 2, 4, and 8, based on subject daily diary
- The change from baseline in serum CRP levels at Weeks 2, 4, and 8
- The change from baseline in fecal calprotectin levels at Week 8

The proportion of subjects with endoscopic improvement will be analyzed using the same statistical method used for the primary efficacy analysis.

The proportion of subjects in clinical remission at Weeks 2, 4, and 8 will be analyzed by the generalized estimating equations (GEE) approach as longitudinal binary outcomes. The model will include treatment, time, and treatment- by-time interaction. The clinical remission rates and odds ratio will be estimated for each time point. The overall treatment difference over 8 weeks will be estimated as the main effect for treatment in the model. The missing values will be imputed as non-remission, and an unstructured working correlation matrix will be used.

The time to normal stool patten will be analyzed using the same statistical method used for the analysis of the time to cessation of rectal bleeding.

The change from baseline in rectal bleeding score and serum CRP levels at Weeks 2, 4, and 8 will be analyzed by repeated-measures analysis of covariance (ANCOVA) models that include treatment, time, and treatment-by-time interaction as fixed effects, and the corresponding baseline value as a covariate. The adjusted changes from baseline and their difference between treatment groups will be estimated for each time point. The overall treatment difference over 8 weeks will be estimated as the main effect for treatment in the model. The missing values will be left as missing, and an unstructured correlation matrix will be assumed.

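### Clinical remission and endoscopic improvement are analysed without the baseline scores that are already collected, which gives up some power and some precision of the rate difference

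*Protocol*

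**What the plan says.** **Clinical remission (Weeks 2, 4, 8).** Besides a bleeding score of 0, the protocol's Secondary Endpoints require stool frequency to be "0 or 1 with at least 1 point decrease from baseline for stool frequency in the Clinical Response Score subset". The SAP (2.2.3) makes the grouping explicit: the one-point fall attaches to a score of 1, not to a score of 0. Protocol 9.6.3 specifies GEE: "The model will include treatment, time, and treatment- by-time interaction". SAP 9.3.2 repeats this, counts missing values as non-remission and uses an unstructured working correlation.

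**Endoscopic improvement (Week 8).** This is a score of 0 or 1 with at least a one-point fall. SAP 9.3.2: "The proportion of subjects with endoscopic improvement will be analyzed using the same statistical method used for the primary efficacy analysis". Under SAP 9.2.1 that method is a chi-square test without continuity correction, plus an odds ratio with Woolf's interval.

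**Baseline elsewhere in the plan.** Stool and bleeding scores come from 3-day recall at Visit 0 (protocol 6.2.2). The central reader scores the screening endoscopy, and entry requires at least 2 (protocol 3.1.1, 4.1.1). The SAP models for bleeding score, CRP and calprotectin (9.3.2) and for IBDQ (9.4.1) all carry the baseline value as a covariate. Protocol 4.2 describes no stratified randomisation. The Mantel-Haenszel analyses in SAP 9.2.2 cover the primary endpoint only; they list severity of UC as a factor, but not these scores.

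**The concern.** How hard the target is depends on where the subject starts. For stool frequency this is built into the definition. For bleeding (target 0) and endoscopy (target 0 or 1) the target is the same for everyone, but a subject starting at 3 has further to go than one starting lower. If the starting score predicts the outcome, leaving it out costs power and leaves chance imbalance between arms uncorrected.

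The plan is also uneven. Rectal bleeding at Weeks 2, 4 and 8 is baseline-adjusted when analysed as a change score, but not when it enters clinical remission at the same visits. No reason is given.

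**Working it through.** **1. The plan's own power figure.** Protocol 9.1 states that Week 8 remission rates "were assumed as 36% and 18%, respectively" and that "a sample size of 110 randomized subjects per group will provide at least 85% power". With p̄ = 0.27:

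z = [0.18√110 − 1.96√(2 × 0.27 × 0.73)] / √(0.36 × 0.64 + 0.18 × 0.82) = (1.888 − 1.231) / 0.615 = 1.07, so power = 85.7%.

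The statement reproduces. It concerns the primary endpoint only; the documents give no rates or power for the two endpoints discussed here.

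**2. What the definitions do.**

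| Component | Baseline | Week 8 scores that qualify |
|---|---|---|
| Stool frequency (SAP grouping) | 0 or 1 | 0 |
| Stool frequency | 2 or 3 | 0 or 1 |
| Rectal bleeding | any | 0 |
| Endoscopy (eligible subjects) | 2 or 3 | 0 or 1 |

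Only stool frequency depends on baseline by definition. Because entry requires an endoscopic score of 2 or more, every Week 8 score of 0 or 1 is already a fall of at least one point. The entry rule (Modified Mayo 4 to 10, endoscopy at least 2) admits all 16 combinations of baseline stool and bleeding scores, so the permitted spread is the whole scale. How common each combination is, the documents do not say.

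**3. Size under a simple assumption.** Assumed: marginal rates borrowed from the primary endpoint (36% v 18%), 110 per arm, one binary baseline stratum, a common conditional odds ratio.

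Worked case, stratum in 30% of subjects with baseline-outcome odds ratio 5:
- Rates by stratum are 10.2% and 36.2% on placebo, 24.8% and 62.2% on mesalamine. The conditional odds ratio is 2.90; the marginal one is 2.56.
- Variance of the rate difference, unadjusted: (0.2304 + 0.1476)/110 = 0.003436.
- Standardised over baseline: (0.2010 + 0.1334)/110 + 0.7 × 0.3 × (0.260 − 0.146)²/220 = 0.003052, which is 11% lower.
- SE of the log odds ratio, unadjusted: √[1/(110 × 0.2304) + 1/(110 × 0.1476)] = 0.318.
- Conditional: stratum information 4.73 + 3.84 = 8.57, so 1/√8.57 = 0.342, which is larger.

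| Stratum share | Baseline OR | Power, chi-square | Power, stratified Mantel-Haenszel | Variance cut, rate difference | SE of conditional log OR (unadjusted 0.318) |
|---|---|---|---|---|---|
| 30% | 1 | 85.7% | 85.6% | 0% | 0.318 |
| 30% | 2 | 85.8% | 86.3% | 2% | 0.322 |
| 30% | 3 | 85.9% | 87.5% | 5% | 0.328 |
| 30% | 5 | 85.9% | 89.6% | 11% | 0.342 |
| 50% | 2 | 86.3% | 86.9% | 2% | 0.322 |
| 50% | 3 | 86.0% | 87.6% | 5% | 0.328 |
| 50% | 5 | 85.6% | 89.2% | 10% | 0.338 |

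Power is from 20,000 simulated trials per row.

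**4. Endoscopic improvement.** Assumed: conditional odds ratio 2.1, half the subjects at baseline 3, 110 per arm, 20,000 trials per row.

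| Placebo response, baseline 2 v 3 | Chi-square | Stratified Mantel-Haenszel |
|---|---|---|
| no gap | 0.784 | 0.781 |
| 40% v 30% | 0.762 | 0.769 |
| 45% v 20% | 0.697 | 0.730 |
| 50% v 15% | 0.608 | 0.681 |

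Null rejection was 0.047 to 0.052. A separate set of assumed gaps (5,000 trials each) gave 0.73 to 0.75, 0.66 to 0.71 and 0.57 to 0.65; the last, 8 points, is the largest gain seen. Across endoscopic settings the variance of the standardised rate difference fell by 0 to 16%, while the SE of the log odds ratio rose, for example from 0.283 to 0.312.

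**5. Clinical remission.** A single-visit logistic simulation (about 25% v 40%, assumed baseline distributions, 1,500 trials per setting) gave a 14% lower variance of the rate difference and power 0.69 to 0.73. With 30 to 50% of recall baselines off by a point, the variance cut was 7 to 9%; power in the noisiest case went from 0.67 to 0.69. Each power figure has a Monte Carlo SE of about √(0.7 × 0.3/1500) = 0.012. This is not the planned three-visit GEE, so it shows direction and rough size only.

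**The case against.** **Endoscopic improvement has no effective baseline clause.** This stands. A reader might infer from the one-point wording that a subject's own baseline decides the classification; for anyone who meets the entry rule it does not. The case for stratifying on 2 v 3 is prognostic, and the documents give no figure for it.

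**The planned odds-ratio intervals would not narrow.** This stands too. A reader might infer that leaving out baseline widens the reported intervals, but on the odds-ratio scale adjustment raises the standard error, as steps 3 and 4 show. The odds ratio itself moves away from 1, so power still rises. A precision gain appears only for a rate difference, which the SAP does not currently plan for either endpoint.

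**Adjustment is not free.** The target changes from a marginal to a conditional odds ratio, and a missing baseline needs a rule. What is free is the data.

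**A linear stool-frequency term may recover little.** The rule is stricter for a baseline of 1 than for 2, against the usual severity gradient. In one illustrative ordinal model the stool component was met by 65%, 79% and 65% at baselines 1, 2 and 3. This stands and shapes the fix.

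**The inputs are assumed and the stakes are low.** Both true. Baseline stool and bleeding are 3-day recall up to 21 days before dosing, while later scores come from the diary, which weakens the likely gain. Both endpoints are tested without multiplicity adjustment (SAP 9.1), and chance imbalance will be visible in the baseline tables (SAP 7.1.2). Using the primary method for endoscopic improvement is a defensible choice for consistency. None of this gives a reason to leave the scores out: with no prognostic gap, the cost in power was within simulation error.

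**Conclusion.** The point holds as a modest efficiency and consistency improvement. Both endpoints lack a baseline term; the scores are collected; the SAP's continuous efficacy models all use baseline. Clinical remission depends on baseline stool frequency by definition, while baseline bleeding and baseline endoscopic score are plausibly prognostic only.

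The loss is about zero if baseline is not prognostic, about half a power point at a baseline odds ratio of 2, about 4 points at an odds ratio of 5, and at most about 8 in the strongest assumed endoscopic setting. On the rate-difference scale the variance cut is 0 to 16% across the settings tried. All of this rests on assumed rates, baseline distributions and prognostic strength.

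A reader might go further and doubt the planned tests. The documents do not support that: under randomisation the unadjusted comparisons are valid, and simulated null rejection stays near 0.05. Priority is low.

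**What to change.** Before unblinding, amend SAP 9.3.2 and protocol 9.6.3 together, since SAP section 12 declares no departure from the protocol's analyses.

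- **Clinical remission:** add baseline rectal bleeding and baseline stool frequency to the GEE, with stool frequency as categories because its effect need not be monotone. Report remission rates and differences at each visit standardised over the ITT set, and label the odds ratios as conditional.
- **Endoscopic improvement:** use a Mantel-Haenszel test stratified by baseline central endoscopic score (2 v 3). Report a stratified or standardised rate difference beside the stratified odds ratio.
- **Both:** state how a missing baseline score is handled so that every ITT subject stays in the analysis, and keep the unadjusted results as supportive.

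The cost is SAP and protocol wording and a few lines of code, with no new data. The downside is that the adjusted odds ratio is conditional on baseline and its log-scale standard error is slightly larger, which is why the standardised rates should sit beside it.

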### 3 INVESTIGATIONAL PLAN

#### 3.1 Overall Trial Design

##### 3.1.1 Overall Design and Control Methods

This is a randomized, double-blind, placebo-controlled, parallel-group, multicenter, international, phase 3 trial to investigate the safety and efficacy of mesalamine 4 g extended release granules (sachet) for the induction of clinical and endoscopic remission in subjects with active, mild to moderate UC. Following completion of Visit 0/screening, the subjects will be randomized to 1 of 2 treatment groups during Visit 1/baseline. Each subject will receive a total of 8 weeks of double-blind treatment with either:

- one mesalamine 4 g extended release granules (sachet) QD (4 g/day) *OR*
- one 4 g placebo sachet to match mesalamine extended release granules (sachet)

Doses will be administered QD at least 1 hour before or at least 2 hours after a meal at approximately the same time each day. The sachet will be emptied on the tongue and swallowed with at least 8 ounces (240 mL) of water. Following randomization, the first dose of investigational medicinal product (IMP) will be administered at the site during Visit 1.

Subjects will visit the trial site 4 times during the double-blind part of trial for safety and efficacy evaluations: baseline and Weeks 2, 4, and 8. On a daily basis, subjects will record clinical symptoms (stool frequency and rectal bleeding) in an electronic diary. The Clinical and Endoscopic Response Score assessments and PGA will be performed at screening/baseline and Week 8. After 8 weeks of treatment, subjects will be evaluated for remission, defined as a Clinical and Endoscopic Response Score of rectal bleeding score of 0 and stool frequency score of 0 or 1 with at least 1 point decrease from baseline, with an endoscopic score of 0 or 1. Whereas, subjects will have only a Clinical Response Score assessment at Weeks 2 and 4.

If subjects discontinue the double-blind treatment before Week 8, the subjects will complete the double-blind end-of-treatment assessments and will be treated via investigator's decision with local standard of care.

Subjects who are found to be worse, defined by an increased number of bowel movements (BM), blood in the stool, abdominal pain and distention, or clinically relevant changes in laboratory chemistry and/or hematology on or after Week 2 will be offered early escape during the trial before Week 8 and will be treated by local standard of care. Subjects who complete Week 8 but fail to meet the defined criteria for remission will be given an option to receive open-label treatment with mesalamine 4 g extended release granules (sachet) for 8 additional weeks in the current trial. If subjects do not opt to receive the 8-week open-label mesalamine treatment, they will be treated by local standard of care. If subjects opt to receive the additional 8-week open-label mesalamine treatment, they will continue with daily diary entries and visit the trial site at 10 and 16 weeks, with only a Clinical Response Score assessment at Week 10, and a Clinical and Endoscopic Response

Score assessment performed at Week 16 in order to determine the subject's eligibility for entry into the maintenance trial (Study 000175).

[figure not shown]
Flexible sigmoidoscopy/colonoscopy will be video recorded and transferred to the independent central reader. The details of the tools, recording, data transfer, and assessment will be documented in an Imaging Charter. The flexible sigmoidoscopy/colonoscopy recording during screening will be sent to the independent central reader for final determination of eligibility, regardless of the local site's score. A flexible sigmoidoscopy/colonoscopy will also be performed at Weeks 8 and 16 as applicable. These recordings will also be sent to the independent central reader for endoscopic endpoint scoring.

Subjects from either treatment group who meet the defined remission criteria after the 8-week double-blind treatment period will be allowed to enroll into a double-blind trial investigating maintenance therapy of mesalamine 2 g extended release granules (Study 000175). Those subjects who do not achieve remission after the 8 additional weeks of open-label treatment will not be enrolled into Study 000175 and will be treated with the local standard of care.

### **3.1.2 Trial Design Diagram**

The trial design is displayed in [Figure 1](#).

**Figure 1: Trial Design Diagram**

D = Day, V = Visit; Wk = Week

### **3.1.3 Trial Schedule**

First subject first visit is expected to occur in the third quarter of 2015 and last subject last visit is expected in the third quarter of 2017. For each subject, the total time in trial from screening (within 21 days before dosing) will be approximately 71 days. For subjects opting to participate in the 8-week open-label period, the total time in the trial will be approximately 126 days.

### **3.2 Planned Number of Trial Sites and Subjects**

This trial will be conducted at approximately 110 sites in North America and Europe. Approximately 220 subjects with active, mild to moderate UC will be randomized to receive mesalamine 4 g extended release granules (sachet) or matching placebo in a 1:1 ratio (110/treatment regimen).

### **3.3 Interim Analysis**

No interim analysis is planned for this trial.

### **3.4 Data Monitoring Committee**

No data monitoring committee will be established for this trial.

### **3.5 Discussion of Overall Trial Design and Choice of Control Groups**

#### **3.5.1 Trial Design**

This is a randomized, double-blind, placebo-controlled, parallel-group, multicenter, international phase 3 trial. Following completion of Visit 0/screening, subjects will be randomized in a 1:1 ratio during Visit 1/baseline to receive either mesalamine 4 g extended release granules (sachet) or matching placebo.

#### **3.5.2 Selection of Endpoints**

The endpoints selected are similar to those used in other clinical studies of mesalamine oral formulation in UC.

#### **3.5.3 Blinding**

This is a randomized, double-blind, placebo-controlled trial. For more information on blinding, see Section 5.5.

#### **3.5.4 Selection of Doses in the Trial**

The well accepted oral dosage for mesalamine induction of remission ranges from 2.4 g to 4.8 g/day. In this trial, the sponsor will utilize the 4 g/day dose of mesalamine 4 g extended release granules (sachet), which is consistent with the approved dose of the marketed mesalamine product for the induction of remission and the treatment of mild to moderate active UC.

### **3.5.5 Selection and Timing of Dose for Each Subject**

Each subject will be randomized to receive either mesalamine 4 g extended release granules (sachet) QD or matching placebo QD. Doses will be administered at least 1 hour before or at least 2 hours after a meal at approximately the same time each day. The sachet will be emptied on the tongue and swallowed with at least 8 ounces (240 mL) of water. Following randomization, the first dose of IMP will be administered at the site during Visit 1.

Subjects who do not meet the defined criteria for remission at Week 8 will be given an option to receive open-label treatment with mesalamine 4 g extended release granules (sachet) for 8 additional weeks in the current trial. The first dose of IMP will be administered the day following the end of double-blind treatment. If subjects do not opt to receive the 8-week open-label mesalamine treatment, they will be treated by local standard of care.

